# VVC/Telephone Baseline Visit Procedures

Staff will conduct the 2 baseline assessment visits by VVC/telephone following the same protocol as used during in-person visits, except that the 1-leg balance test will not be performed. Certain items needed for the baseline assessment will be mailed to participants prior to the second baseline visit. These items include:

- Wrist actigraph
- 7-day sleep diary
- Hypnotic medication log
- Paper copies of the Trails, Digit Symbol/Symbol Copy tests
- Sleep apnea screening device (e.g., Watch PAT), if STOP-BANG score > 4
- Postage-paid, pre-addressed, insured delivery box ("Return Delivery" Box)

Participants will also have the option to meet staff at a VA GLAHS facility that is near their home to pick-up and return study devices//materials. In those circumstances, staff will meet the participant in a parking lot or lobby to exchange devices, while maintaining social distancing.

If it is determined that the MINI needs to be administered to a participant, a separate VVC visit will be scheduled.

| Table 2: Data Collection Instruments  |                               |   |   | Time point for data collection |      |          |  |
|---|-------------------------------|---|---|--------------------------------|------|----------|--|
| Instrument NAME   | Standard or
Study-Specific | Purpose   |   | Intervention                   | Post | 6-months |  |
|   | Standard                      | Self-reported   |   |                                |      |          |  |
| Self-Administered Comorbidity  Questionnaire                                     |                               |   | X |                                |      |          |  |
| Insomnia Severity Index (ISI)    | Standard                      | Insomnia symptoms severity  |   | Х                              | Х    | Х        |  |
| Pittsburgh Sleep Quality Index (PSQI)    | Standard                      | Self-reported sleep quality   |   | X                              | Х    | Х        |  |
| Dysfunctional Beliefs and Attitudes about Sleep – 16 item (DBAS-16)              | Standard                      | Beliefs about insomnia  |   |                                | Х    | Х        |  |

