| Alcohol, Smoking and Substance
Involvement Screening Test
(ASSIST)         | Standard                      | Screens for substance abuse   |   |                                |      |          |  |
| Trails A & B tests   | Standard                      | Mental processing speed, attention, executive functioning   | Х |                                | Х    | Х        |  |
| Digit Symbol Substitution and Symbol Copy                                        | Standard                      | Mental processing speed and attention   | Х |                                | Х    | Х        |  |
| Mini-Mental State Examination (MMSE)   | Standard                      | Cognitive status  | Х |                                | Х    | Х        |  |
| One-leg standing balance   | Standard                      | Balance measurement   | Х |                                | Х    | Х        |  |
| Benzodiazepine Dependence Questionnaire (DBEP)35  | Standard                      | Symptoms of benzodiazepine dependence   | Х |                                | Х    | Х        |  |
| Clinical Institute Withdrawal
Assessment Scale –
Benzodiazepines (CIWA-B)  | Standard                      | Symptoms of benzodiazepine withdrawal   | x | x                              | х    | х        |  |
| Credibility/expectancy
questionnaire (CEQ)                                    | Standard                      | Self-reported confidence in treatment   | × | Х                              | X    | ×        |  |
| Demographic questions   | Study-specific (attached)     | Characteristics of participants (e.g., marital status, living location, employment)   | х |                                |      |          |  |

| Fall event question                  | Study-specific (attached) | History of slips/trips/falls   | Х |   | Х | Х |
|--------------------------------------|---------------------------|--|---|---|---|---|
| ICSD-3 questions                     | Study-specific (attached) | Symptoms of insomnia based on ICSD-3 criteria  | Х |   | Х | Х |
| Additional comorbidity questions     | Study-specific (attached) | Self-reported medical/psychological conditions                                       |   |   |   |   |
| Nighttime urinary symptoms questions | Study-specific (attached) | Frequency and impact of nighttime urination  | Х |   | Х | Х |

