# Amendment for telehealth option

Post-treatment follow-up assessment (begins at end of session 8)

Prior to intervention session 8 VVC visit, participants will receive by mail/pick-up the following items:

- Wrist actigraph
- Sleep diary
- Questionnaire packet
- Medication log
- Fall log
- Postage-paid return, insured Return Box to return the study materials (e.g.,actigraph)

Participants will also be instructed to go to the VA clinical laboratory to provide a urine sample.

At the end of session 8, the participant will be instructed to put on the actigraph to wear at home for 1 week and to complete the sleep and medication diary each day of that week.

One week later, a VVC post-treatment assessment visit will occur. At that visit, the participant will be administered selected questionnaires included in the baseline assessment. Participants will also be instructed to record any falls they experience over the next six months in the fall log. Participants will mail/deliver the actigraph and sleep diary back to the study office.

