# Primary Analysis Plan

We plan to randomize 132 individuals, of whom we expect 13% to drop out (i.e., fail to complete assessments) by 6-months, yielding N=114 participants with complete data ( $\sim$  57 per group). We base this drop-out on our completed study ([name] VA Merit 08-295). We will include terms for stratification characteristics and covariates for baseline pain intensity, PHQ-9, and opioid use in all of the models. All analyses below assume  $\alpha$ =0.05, power=0.80, two-sided hypothesis tests, and intention-to-treat approach. Effect sizes are in the measure's natural units and Cohen's d (large=.8; medium=.5; small=.2).

- (H1a) Participants who receive MTcap will have increased likelihood of hypnotic discontinuation post-treatment and at 6 months follow-up compared with those who receive SGT+CBTI: Hypnotic discontinuation (yes=1/no=0) will be regressed on treatment group assignment (MTcap vs. SGT+CBTI) in two logistic regression models (post-treatment and 6 months follow-up). Sample size calculations establish that 114 participants will be adequate to detect a difference of 21% to 26% between the MTcap and SGT+CBTI groups, depending upon the discontinuation percentage of the SGT+CBTI group (59% to 63% at follow-up in prior studies). In our feasibility study, 100% discontinued hypnotics post-treatment. We will use multiple imputation.

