- (H1b) Participants who receive MTcap will use less hypnotic medication post-treatment and at 6 months follow-up compared with those who receive SGT+CBTI: Two outcomes will be assessed: frequency (i.e., 0 to 7 days used) and quantity (i.e., average daily dose in diazepam milligram equivalents). For each outcome, we will fit a 2 (group) by 3 (time) general linear mixed model. Interaction terms will be used to assess the change in the outcome (baseline→post-treatment, baseline→6 months) for MTcap vs. SGT+CBTI. Power Analysis: We use statistics from our recent study, which found a baseline to 6-month correlation of *r*=0.83 (95% Cl=0.77-0.88) and a standard deviation (SD) of 1.94 for a similar outcome measure—"days used of medications commonly used for insomnia" (0 to 7 days used). Assuming r=0.83 and n=57 per group, we could detect a treatment effect of 0.60 (Cohen's *d*=0.30) (i.e. a difference of 6/10ths of a day between the groups). Assuming *r*=0.77 (i.e., using the LCL), we could detect a treatment effect of 0.70 days (Cohen's *d*=0.36). If we disregard data from our recent study, power calculations still show that we could detect a treatment effect of 1.02 days (Cohen's *d*=.53; i.e., detect a difference of 1 day between groups). For quantity of use, power calculations indicate that we could detect a treatment effect of *d*=.53 (medium effect).
- (H2) Participants who receive MTcap will have lower Insomnia Severity Index scores at 6 months follow-up compared to SGT+CBTI: We will fit a general linear mixed model, and an interaction term will assess the change in ISI from baseline to 6 months for MTcap vs. SGT+CBTI. Power Analysis: Our prior research shows an ISI SD=5.3 and *r*=0.39 (95% CI=0.24-0.52) between baseline ISI and 6 month follow-up ISI. Assuming this correlation and a sample size of N=57 per group, the study could detect an effect as small as 3.1 units on the ISI (or a Cohen's *d*=.58). Assuming *r*=0.24 (i.e., using the LCL), we could detect an effect as small as 3.43 units on the ISI (or a Cohen's *d*=.65). An effect of 4.0 units on the ISI has been

- determined to be clinically-meaningful in prior research, 103 which means that the proposed study would be able to detect effects that are clinically-meaningful (as well as effects that smaller than clinically-meaningful); both of these power analyses suggest that the study could detect effects that are between medium and large effects.

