- (H3) Dysfunctional Beliefs and Attitudes About Sleep (DBAS) Medication Scale ratings will improve compared to SGT+CBTI post-treatment and at 6 months follow-up: We will fit a 2 (group) by 3 (time) general linear mixed model. Interaction terms will be used to assess the change in DBAS medication items (baseline→post-treatment, baseline→6 months) for MTcap vs. SGT+CBTI group. Power Analysis: Our prior research shows a DBAS-16 SD= 2.1 and *r*=0.55 (95% CI=0.39,0.64) between baseline DBAS and 6-month follow-up DBAS. Assuming this correlation and a sample size of N=57 per group, the study could detect an effect size of *d*=0.50, which is a difference of 1.1 units on the DBAS-16. Assuming *r*=0.39 (the LCL), we could detect an effect size of *d*=.58, corresponding to a 1.2 unit change.

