# Secondary Analysis Plan (H4)

[figure not shown]
We will test whether MTcap improves cognition (DSS, Symbol Copy; Trails A & B) and balance (One-leg balance) at post-treatment and 6-month follow-up, using general linear mixed model (see Hypothesis 3 above). Effect size calculations: For the most pessimistic case—no correlation between these measures at the two time points—a post-test only analysis could detect a difference of *d*=0.52.

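### The H4 detectable effect of d=0.52 is for a post-test comparison; the planned change-from-baseline interaction detects only about 0.74 to 0.75 at the plan's own zero correlation

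*Combined protocol and SAP*

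**What the plan says.** The Secondary Analysis Plan (H4) tests cognition and one-leg balance at post-treatment and 6 months, "using general linear mixed model (see Hypothesis 3 above". The H3 paragraph of the Primary Analysis Plan defines that model as group (2) by time (3) and names the test: "Interaction terms will be used to assess the change in DBAS medication items", from baseline to each follow-up. H2 is set up the same way: "an interaction term will assess the change in ISI from baseline to 6 months for MTcap vs. SGT+CBTI".

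The only sensitivity statement for H4 assumes no correlation between the two time points. It says that "a post-test only analysis could detect a difference of" d=0.52 and presents this as the worst case. No correlation or detectable effect is given for the interaction itself.

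Besides the stratification terms, the Primary Analysis Plan specifies "covariates for baseline pain intensity, PHQ-9, and opioid use in all of the models". The baseline value of the outcome is not among them.

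For balance, Table 2 schedules "One-leg standing balance" at baseline, post-treatment and 6 months. The VVC/Telephone Baseline Visit Procedures say that remote baseline visits follow the in-person protocol "except that the 1-leg balance test will not be performed". At the remote post-treatment visit, "the participant will be administered selected questionnaires included in the baseline assessment"; the remote follow-up text does not say whether balance is tested.

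**The concern.** The plan names one contrast for H4 and reports the sensitivity of another. A change score carries the variability of two measurements. When these are uncorrelated, subtracting the baseline adds noise and removes none, so zero correlation is kinder to a post-test comparison than to a change contrast.

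The plan's own figures show the inconsistency. With the same 57 per arm and the same kind of test, H2 states d=0.65 at a correlation of 0.24. A lower correlation cannot bring the detectable effect down to 0.52.

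Balance and cognition are the stated secondary aim. If a null H4 result is read against d=0.52, readers will credit the test with a sensitivity it may not have. For balance, the assumed 57 per arm is also optimistic to the extent that baselines are done remotely.

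**Working it through.** **Inputs.** Primary Analysis Plan: two-sided alpha 0.05, power 0.80, 132 randomised, 13% dropout by 6 months, about 57 per arm with complete data. Randomization section: 66 per arm, randomised after the baseline assessment. H4: correlation r=0.

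**Step 1: reproduce the stated figure.** For a post-test comparison, d = (1.960 + 0.842) × sqrt(2/57) = 2.802 × 0.1873 = 0.525. The noncentral t (112 df) gives 0.529. Normal-approximation power at d=0.52 with 57 per arm is 79.3%. So 0.52 is correct, within rounding, for the analysis it names.

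**Step 2: identify the plan's formula for the interaction tests.** A change contrast multiplies the post-test figure by sqrt(2(1−r)); a baseline-adjusted contrast multiplies it by sqrt(1−r²). Normal approximation, 57 per arm:

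| Hypothesis | r | Stated d | Change contrast | Baseline-adjusted |
|---|---|---|---|---|
| H1b | 0.83 | 0.30 | 0.306 | 0.293 |
| H1b | 0.77 | 0.36 | 0.356 | 0.335 |
| H2 | 0.39 | 0.58 | 0.580 | 0.483 |
| H2 | 0.24 | 0.65 | 0.647 | 0.509 |
| H3 | 0.55 | 0.50 | 0.498 | 0.438 |
| H3 | 0.39 | 0.58 | 0.580 | 0.483 |

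The change-contrast formula matches every stated value to within 0.01. The baseline-adjusted formula does not.

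**Step 3: apply the same formula to H4 at r=0.** sqrt(2) × 0.525 = 0.742 (normal); sqrt(2) × 0.529 = 0.749 (t).

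A mixed model can also use the nine participants per arm who have only a baseline value. With 66 baselines and 57 follow-ups, the variance per arm is (1−r²)/57 + (1−r)²/66 in SD² units. At r=0, d = 2.802 × sqrt(2 × (1/57 + 1/66)) = 0.716. The information matrix of the unconstrained 2-by-3 model gives the same value.

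**Step 4: power of the planned interaction at d=0.52.** The correlations are those the plan quotes for other measures, used here as a range; none is stated for an H4 measure.

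| r | 57 per arm (t) | 66 baselines, 57 follow-ups (normal) |
|---|---|---|
| 0 | 49% | 53% |
| 0.24 | 61% | 64% |
| 0.39 | 70% | 73% |
| 0.55 | 83% | 84% |

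At r=0.77 with 57 per arm, power is 98%. Power reaches 80% at r of about 0.51 (normal) or 0.52 (t) with 57 per arm, and at about 0.49 with all baselines. At r=0, 80% power for d=0.52 would need 4 × 2.802² / 0.52² = 116.1, so about 117 per arm.

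**Step 5: the analysis that would fit the stated figure.** A baseline-adjusted comparison with 57 per arm detects 0.529 × sqrt(1−r²): 0.529 at r=0 and 0.487 at r=0.39 (t). Its power at d=0.52 is 79% and 85% respectively. For this analysis r=0 really is the worst case.

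**Step 6: balance.** A participant with a remote baseline has no observed baseline balance value and so no observed change. The documents do not give the split between remote and in-person baselines, so the shortfall cannot be computed.

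**The case against.** The strongest reply is that the plan makes no arithmetic error. It labels 0.52 as a post-test figure, and the figure is right for that. One can read the sentence as a bound: if baseline carries no information, drop it and compare follow-up values. The Specific Aims word the secondary hypothesis as better balance and cognition at follow-up, which suits such a comparison. H1b similarly gives d=0.53 when prior data are set aside. If baseline means were constrained equal, or the baseline outcome were a covariate, about 0.525 would be correct.

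This shows how easily the plan could be made consistent, but not that it is. The H4 text points to the H3 model and its change interaction, and specifies neither a constrained baseline nor the baseline outcome as a covariate.

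Several limits do stand:

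- Zero correlation is the plan's worst case, not its expectation. Two of its three point estimates for other measures (0.55 and 0.83, against 0.39) lie above the level where the shortfall disappears.
- An intention-to-treat mixed model would use all observed baselines, so 0.72 is arguably nearer than 0.74 to 0.75. Post-treatment retention is not stated; with all 66 per arm at both times, the r=0 figure would be 2.802 × sqrt(4/66) = 0.69.
- The sample size of 132 does not rest on H4.
- The balance shortfall is unquantified. The Setting paragraph lets staff meet participants for assessments if necessary, so some otherwise remote participants may be tested. The UCLA Health data described under the exploratory analyses may add participants, but no number is given.

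**Conclusion.** The concern holds. The stated d=0.52 is correct for a post-test comparison but is not the worst case for the planned H4 test. At the plan's own zero correlation, the interaction detects about 0.74 to 0.75 with 57 per arm, or 0.72 with all 66 baselines, and has about 49% to 53% power at 0.52. This assumes an unconstrained baseline, the natural reading of a 2-by-3 model tested through its interaction terms. The shortfall applies only when the correlation is below about 0.5; above that, the planned test does at least as well as stated. The documents do not say which side of that line the cognition and balance measures fall on. For balance, any remote baselines without a balance value further reduce the number with observed change, by an unknown amount. The point should be corrected, but it concerns a secondary aim and does not affect the sample size.

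**What to change.** Choose one of two wordings for H4:

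1. Analyse each measure as a baseline-adjusted group difference, by a constrained-baseline mixed model or ANCOVA, and state about d=0.53 as the worst case with 57 per arm. This is the better choice: it is at least as precise as the change contrast, and the constrained-baseline model can also use follow-up balance values from participants with no baseline value.
2. Keep the interaction and restate the zero-correlation figure as about d=0.74 to 0.75 (0.72 if all 66 baselines per arm are counted).

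In either case, base the balance figure on the number expected to have balance data, state whether one-leg balance is tested at remote follow-up, and reconcile this with Table 2.

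The cost is SAP wording: one sentence naming the H4 contrast and its detectable effect, and one on balance at remote visits. No new participants or procedures are needed.

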# Exploratory Analysis Plan (E1)

We will describe the frequency of falls in each arm. We will test whether MTcap is associated with not falling, using logistic regression (dependent variable [DV] is fall [binary]), which will be predicted as a function of treatment group assignment. E2: Mediation analyses to elucidate the relationship between insomnia severity, hypnotic use, and balance will be conducted using a statistical macro developed by UCLA, which simultaneously tests for the associations of the independent variable (IV; ISI) on the DV (balance), IV on the mediator (hypnotic dose in diazepam equivalents), and IV (ISI) plus mediator (hypnotic dose) on DV (balance) (Sobel, Goodman, and Goodman II tests). Similar mediation analyses (using a Stata user written command for binary mediation) will be performed for the DV, history of fall.

Amendment: We will conduct the same analyses above, but with the addition of data from participants recruited and seen at the UCLA Health site. These data will be transferred in a limited data set from UCLA Health to VA Greater Los Angeles under an approved data use agreement.

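### The exploratory balance mediation analysis relies on three normal-theory tests of the indirect effect; a percentile bootstrap interval would be more powerful if the paths are small to moderate

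*Combined protocol and SAP*

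**What the plan says.** The mediation work (E2) sits in the combined protocol and SAP under "Exploratory Analysis Plan (E1"). ISI is the independent variable, balance the dependent variable and hypnotic dose the mediator. The macro is to fit, among other paths, the "IV on the mediator (hypnotic dose in diazepam equivalents"), and the indirect effect is tested by "Sobel, Goodman, and Goodman II tests". No bootstrap or other resampling interval is mentioned, and nothing says which test decides if they disagree.

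Falls are handled separately: "Similar mediation analyses (using a Stata user written command for binary mediation) will be performed for the DV, history of fall". No test or interval method is given there.

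The sample size comes from the Primary Analysis Plan: "We plan to randomize 132 individuals", "of whom we expect 13% to drop out", "yielding N=114 participants with complete data". That section also sets "0.05, power=0.80, two-sided hypothesis tests" for the analyses that follow it, but no path size, detectable effect or power is attached to E2.

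**The concern.** The indirect effect is the product of path a (ISI to dose) and path b (dose to balance, given ISI). At moderate sample sizes the estimated product is skewed unless at least one path is large relative to its standard error. Sobel and the two Goodman versions all divide the product by a standard error and use normal critical values. They differ only in whether the product of the two squared standard errors is left out, added or subtracted. When the paths are small this has two effects: the tests reject too rarely, and a symmetric interval sits too low for a positive effect. A modest mediated path could be missed that another method, applied to the same data, would find. Naming three tests without a governing one also leaves the conclusion open when they differ.

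**Working it through.** **Planned N.** 132 × (1 − 0.13) = 114.84, which agrees with the plan's 114.

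**Inputs.** N = 114 and two-sided α = 0.05 are from the Primary Analysis Plan. Path sizes are not in the documents, so a range from 0 to 0.59 is assumed, with a unit-variance predictor and unit-variance residuals. The coefficients are then close to standardised ones.

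**Hand check.** Write z_a = a/SE_a and z_b = b/SE_b. Then

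- Sobel z = ab / √(a²SE_b² + b²SE_a²) = z_a z_b / √(z_a² + z_b²).
- With a = b and both standard errors about 1/√114 = 0.0937, this reduces to z_a/√2.
- Sobel therefore reaches 1.96 only when each path has z = 1.96 × √2 = 2.77, that is, a path estimate of 2.77 × 0.0937 = 0.26. Each path alone is significant from 1.96 × 0.0937 = 0.18.

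Between about 0.18 and 0.26 both paths can be individually significant while Sobel is not. That is where the conservatism bites.

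**Simulation.** 1,500 data sets per setting, N = 114, normal errors, least-squares paths, no direct effect, 800 bootstrap resamples. The Monte Carlo standard error is at most √(0.5 × 0.5/1500) = 1.3 points. Power in %:

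| a = b | Sobel | Goodman (term added) | Goodman II (term subtracted) | Percentile bootstrap | Bootstrap minus Sobel |
|---|---|---|---|---|---|
| 0.14 | 2.3 | 2.2 | 3.3 | 8.7 | 6.4 |
| 0.20 | 12.2 | 10.1 | 14.4 | 29.4 | 17.2 |
| 0.26 | 37.7 | 34.4 | 41.7 | 58.7 | 21.0 |
| 0.30 | 58.6 | 54.9 | 62.7 | 75.5 | 16.9 |
| 0.35 | 81.3 | 79.1 | 83.9 | 91.1 | 9.8 |
| 0.39 | 92.9 | 91.0 | 94.2 | 96.1 | 3.2 |
| 0.59 | 100 | 100 | 100 | 100 | 0 |

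A repeat gave 12 against 28 (0.20), 38 against 57 (0.26) and 59 against 76 (0.30), so gaps of 16, 19 and 17 points. Across all repeats, including runs with a direct effect of 0.14, the gap at 0.20 to 0.30 lay between 14 and 22 points. With unequal paths of 0.26 and 0.39, power was 62.2 against 74.5. At N = 132 it was 47 against 67 (0.26) and 71 against 83 (0.30).

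**Interval placement.** With a = b of 0.20 to 0.30, the true indirect effect lay above the symmetric Sobel interval in 7 to 9% of samples and below it in under 1%. The percentile interval was missed on the high side in 4 to 5%. The nominal rate is 2.5% on each side.

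**Type I error.** With one path zero and the other 0.26, Sobel rejected in 1.1 to 1.3% of samples and the percentile bootstrap in 3.6 to 4.9%. With a = 0 and b = 0.39, Sobel rejected in about 2.7%, the percentile bootstrap in 5.3 to 6.4% across runs, and the bias-corrected bootstrap in 8.7%.

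**Zeros in the mediator.** Follow-up dose may be zero for many participants: the plan cites 59% to 63% discontinuation for the comparator. With 60% of mediator values set to zero (an assumption), Sobel against bootstrap power was 24 against 45 (0.26), 40 against 63 (0.30) and 62 against 77 (0.35). The paths here are those before zeroing. The gap does not disappear.

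**Goodman II variance.** It equals SE_a² SE_b² (z_a² + z_b² − 1), so it is negative when z_a² + z_b² < 1. With both paths zero, that probability is 1 − e^(−0.5) = 39%. By simulation it is 7% at paths of 0.14 and about 1% at 0.20.

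**The case against.** The strongest reply is that Sobel is a recognised, conservative method, that E2 is exploratory with no power claimed, and that the loss rests on path sizes nobody has stated. Most of this stands. It sets the priority, and it means that the size of the loss can only be given as a range. It does not remove the advantage of the bootstrap at small and moderate paths.

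A reader might infer more than the documents support:

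- **That all mediation analyses use Sobel-type tests.** The named tests are attached to balance. For falls only a user-written command is named, and calling the analyses similar does not settle how inference is done.
- **That a real mediated path would probably be missed.** At 0.30 Sobel already has about 59% power, and from 0.39 the choice hardly matters. At 0.20 the bootstrap also misses the path in about 70% of samples.
- **That Goodman II leaves the analysis without a test.** Its variance fails often only when both paths are null or very weak, and two other tests are named beside it.
- **That three tests imply selective reporting.** They are the output of one macro. They disagreed in 5 to 8% of samples at paths of 0.20 to 0.35, so a governing rule is useful, but nothing suggests an intention to choose.
- **That the bootstrap is free.** Part of its gain comes from giving up Sobel's conservatism, and in one null setting its error rate was slightly above 5%.

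**Conclusion.** The point holds for the E2 balance analysis. At about 114 participants, Sobel gives up roughly 16 to 19 points of power to a percentile bootstrap when both paths are 0.20 to 0.30, about 10 at 0.35, about 3 at 0.39 and none at 0.59. Symmetric intervals for small positive effects sit too low.

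This rests on assumed path sizes, on normal errors in the main runs, and on N = 114. The actual N for balance is uncertain. Remote baseline visits omit the one-leg test, which lowers it, and the amendment adding UCLA Health participants raises it; neither number is given.

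It is a cheap improvement of low priority: E2 is exploratory and no primary or secondary conclusion depends on it. Changing the interval method also leaves open a separate matter in E2, namely that the exposure is ISI rather than randomised arm and that the time points of exposure, mediator and outcome are not stated.

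**What to change.** For the balance outcome, replace the three tests with one stated method: a percentile bootstrap 95% confidence interval for the indirect effect, resampling participants and re-estimating both paths each time, with for example 5,000 resamples and a recorded seed. Specify percentile rather than bias-corrected, because the bias-corrected version reached 8.7% type I error in the null setting above. Preferably report the same interval for the fall outcome, where it would fill a gap rather than replace a named test.

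The cost is one sentence in the plan and a little computing, with no new data. The statistical price is a type I error of about 6% when one path is zero and the other moderate, where Sobel gives about 3%. That is acceptable for an exploratory analysis.

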#### Post-treatment assessment

The post-treatment assessment will begin on the same day that the participant completes session 8 of either intervention. At the end of session 8, a participant will be provided with an actigraph to wear at home for 1 week and a sleep and medication diary to complete. When the participant returns the actigraph and diary after 1 week, he/she will be administered selected questionnaires included in the baseline assessment. In addition, a urine sample will be collected to confirm participants' self-report of hypnotic discontinuation. Participants will also be given a six-month fall log to record any falls they experience during the period between the post-assessment and the six-month follow-up assessment. The CURES database will also be queried to obtain data about prescriptions for controlled medications. Participants who complete the post-treatment assessment will receive \$50 for their travel and time.

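### The exploratory mediation analysis (E2) omits treatment arm, names no visits and leaves the fall window open, so follow-up data could give confounded paths and falls that precede their supposed cause

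*Combined protocol and SAP*

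**What the plan says.** The Exploratory Analysis Plan section contains two analyses. E1 is a logistic regression of falling, "which will be predicted as a function of treatment group assignment". E2 is a mediation analysis intended "to elucidate the relationship between insomnia severity, hypnotic use, and balance".

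E2 writes out its regressions. The first two are "the independent variable (IV; ISI) on the DV (balance), IV on the mediator (hypnotic dose in diazepam equivalents"). The third is "IV (ISI) plus mediator (hypnotic dose) on DV (balance) (Sobel, Goodman, and Goodman II tests"). The analysis is then repeated for falls: "Similar mediation analyses (using a Stata user written command for binary mediation) will be performed for the DV, history of fall".

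The Primary Analysis Plan sets a general covariate rule: "We will include terms for stratification characteristics and covariates for baseline pain intensity, PHQ-9, and opioid use in all of the models". Arm is not in that list.

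Two sources of fall data are described. Table 2 has a fall event question, whose purpose is given as "History of slips/trips/falls", marked at baseline, post-treatment and six months. The Post-treatment assessment section describes a "six-month fall log to record any falls they experience during the period between the post-assessment and the six-month follow-up assessment". E2 refers to neither, and it gives no visit for ISI, dose, balance or falls.

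**The concern.** Two features of E2 look wrong.

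**Arm.** Under Specific Aims the trial hypothesises that MTcap lowers hypnotic dose (H1b, both follow-up times), lowers ISI (H2, six months) and improves balance (secondary aim, both follow-up times). If E2 is fitted to follow-up data pooled over arms, arm is an omitted common cause of predictor, mediator and outcome. Pooling then induces ISI-dose and dose-balance associations even if the variables are unrelated within each arm. E1 includes arm and sits in the same section, so the absence from E2 is noticeable. The general covariate rule does not supply it.

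**Time order.** A mediation claim needs the predictor and mediator to come before the outcome. A fall history collected at a visit looks back. If it is paired with dose measured at that visit, the fall can come first. The same happens if six-month dose is paired with the six-month log, because that log covers the months before the six-month visit.

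What is at stake is the reading of an exploratory result on whether hypnotic dose links insomnia to balance and falls. A different test of the indirect effect would cure neither problem.

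**Working it through.** **Inputs from the plan.** 132 randomised 1:1; 13% dropout, giving 114 (57 per group); two-sided 5%; 80% power. Detectable effects: ISI 0.58 SD (H2), dose 0.53 SD (H1b), balance 0.52 SD (secondary analysis).

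**Reproducing the plan's figure.** E2 has no figure of its own; the nearest is d = 0.52 for balance. Detectable d = (1.960 + 0.842) × √(2/57) = 0.525, or 0.529 with the t distribution. Power at d = 0.52 is 0.793. Also 132 × 0.87 = 114.8. The plan's figures reproduce.

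**Correlation induced by arm alone.** With equal arms, within-arm SD 1 and no within-arm relation, r = (d₁d₂/4) / √[(1 + d₁²/4)(1 + d₂²/4)].
- ISI-dose: 0.0769 / √(1.0841 × 1.0702) = 0.071
- dose-balance: 0.0689 / √(1.0702 × 1.0676) = 0.064 in size (negative)
- ISI-balance: 0.0754 / √(1.0841 × 1.0676) = 0.070 in size (negative)

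**Approximate chance that each path is significant.**
- ISI to dose: 0.071 × √111 ≈ 0.75. P(|Z + 0.75| > 1.96) ≈ 0.113 + 0.003 = 0.12.
- Dose to balance given ISI: the partial correlation is about 0.064 − 0.071 × 0.070 ≈ 0.06. Then 0.06 × √110 ≈ 0.63, and P ≈ 0.091 + 0.005 = 0.10.

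**Simulation of E2.** N = 114, 6,000 runs per scenario, normal variables. Dose is regressed on ISI, and balance on dose plus ISI, each with and without arm. The Sobel statistic is ab / √(a²SE_b² + b²SE_a²), where a is the ISI-to-dose coefficient and b the dose-to-balance coefficient. The true indirect effect is zero in every row.

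| Arm effects (SD): ISI, dose, balance | Real within-arm path | Significant without arm | Significant with arm |
|---|---|---|---|
| 0.58, 0.53, 0.52 | none | a 12.2%, b 9.6%, Sobel 0.1% | a 5.4%, b 5.3%, Sobel 0.0% |
| 0.58, 0.53, 0.52 | a only (0.4) | Sobel 5.4% | Sobel 3.5% |
| 0.58, 0.53, 0.52 | b only (−0.4) | Sobel 8.6% | Sobel 3.4% |
| 0.8 each (assumed) | none | a 31.5%, b 25.8%, Sobel 1.6% | a 5.5%, b 5.5%, Sobel 0.0% |
| 0.8 each (assumed) | a only (0.4) | Sobel 11.6% | Sobel 3.2% |
| 0.8 each (assumed) | b only (−0.4) | Sobel 26.5% | Sobel 2.9% |
| 0, 0, 0 (as at baseline) | none | a 5.0%, b 5.2%, Sobel 0.0% | a 4.8%, b 5.2%, Sobel 0.0% |

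In the first row the mean spurious coefficients without arm are 0.072 and −0.060 SD; with arm they are about zero. The falls version was not simulated because the plan gives no fall rate.

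**Time order, by reading.** Three pairings fit E2's text.
1. All variables from one visit: cross-sectional, with fall history looking back.
2. Six-month ISI and dose with the six-month log: the falls come first.
3. Post-treatment ISI and dose with the six-month log or six-month balance: outcome correctly last.

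The text does not choose among them.

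**The case against.** A reader might infer that the trial would report mediation that does not exist. The documents do not support that, for three reasons.

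First, one significant path is not mediation. E2 judges the indirect effect by the Sobel and Goodman tests. At the plan's detectable effects with no real path, Sobel rejects in about 0.1% of runs, far below 5%. The larger rates need a real path on one side, or arm effects above those the plan is powered for.

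Second, the arm distortion is conditional. E2 does not say that it uses post-randomisation data, and its stated purpose is to describe a relationship, not to explain a treatment effect. On baseline data, omitting arm does no harm. H2 also concerns ISI at six months only, so an arm effect on post-treatment ISI is not formally hypothesised.

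Third, the time-order problem is silence, not a stated error. A correctly ordered analysis fits the text. Equating the fall-history outcome with the Table 2 question is an inference, and the recall window may be in the attached form, which is not among the documents. The source of dose is open too: Table 2 lists both a one-week medication log and an abstraction form covering earlier and current use.

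All of this stands and limits the size of the point. It does not remove it. Several readings that the text allows are confounded or reversed in time, and the choice is left to the analyst. A real path on one side is also plausible, since the Specific Aims link hypnotic use to falls.

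**Conclusion.** The point holds in a limited, conditional form. E2 specifies its equations without arm and without visits. If follow-up data are used, omitting arm roughly doubles single-path false positives at the plan's detectable effects (about 5% to 10-12%). The Sobel test is almost unaffected if no path is real. If one path is real it goes from about 3.5% to 5-9%, and to 12-27% with assumed arm effects of 0.8 SD. With baseline data there is no arm distortion. Separately, the undefined fall-history window allows falls to precede the ISI and dose said to cause them, whatever the arm effects.

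The figures assume normal variables, the plan's detectable effects taken as arm differences at one visit, and illustrative values of 0.4 (within-arm correlation) and 0.8 SD (larger arm effect). The analysis is exploratory, and no primary or secondary conclusion depends on it. This is a minor but worthwhile correction.

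**What to change.** Amend the E2 text as follows.

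1. Include treatment arm in both the mediator and the outcome equation whenever post-randomisation data are used.
2. Name the visit and source for each variable so that ISI and dose precede the outcome: for example, post-treatment ISI and dose, each adjusted for baseline, with six-month balance.
3. Take falls from the prospective six-month log, in place of fall history.
4. Since ISI and dose would then come from the same visit, describe the ISI-to-dose path as same-visit and associational.

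No new data or participants are needed. The costs are one more term per equation and the loss of same-visit pairs with the outcome. Post-treatment dose may also vary little if most participants have stopped by then; the Primary Analysis Plan reports 100% discontinuation post-treatment in the feasibility study. If so, the mediator carries little information, and the report should say so.
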